\leq Grade 1	No change	No change
Grade 2	No change	No change
Grade 3	Hold dose until recovery to at least Grade 1, then resume dose at 50%	Dose delay until recovery to at least Grade 1, can resume at same dose*
Grade 4	Hold dose until recovery to at least Grade 1, then resume dose at 50%	Dose delay until recovery to at least Grade 1, can resume at same dose*

*Toxicity criteria for holding daratumumab dose are detailed above in [Section 5.5.1.2](#)

** Participants having \geq Grade 3 AE at a dose $< 25 \text{ mg/m}^2$ should go off study

Dexamethasone

Dexamethasone Toxicity

For management of dexamethasone toxicity see table below. If dexamethasone is permanently discontinued due to toxicity, pre- and post-administration doses administered on the day of daratumumab dosing may be given at the investigators' discretion. This table represents suggested dose modifications of dexamethasone, but physician discretion and clinical judgment should prevail.

Table 5-6

NCI-CTCAE Category	Toxicity	Dose Change
Gastrointestinal	Grade 1-2 dyspepsia, gastric, or duodenal ulcer, gastritis requiring medical management	Treat with H2 blockers, sucralfate, or omeprazole. If symptoms persist despite above measure, decrease dexamethasone dose by 50%.
	≥Grade 3 requiring hospitalization or surgery	Hold dexamethasone until symptoms adequately controlled. Restart at 50% of current dose along with concurrent therapy with H2 blockers, sucralfate, or omeprazole. If symptoms persist despite above measure, discontinue dexamethasone and do not resume.
	Acute pancreatitis	Discontinue therapeutic dose of dexamethasone and do not resume.
Cardiovascular	≥Grade 3 edema limiting function and unresponsive to therapy or anasarca	Diuretics as needed and decrease dexamethasone dose by 25%. If edema persists despite above measures, decrease dose to 50% of initial dose. Discontinue dexamethasone and do not resume if symptoms persist despite 50% reduction.
Neurology/ Psychiatric	≥Grade 2 interfering with function but not interfering with activities of daily living	Hold dexamethasone until symptoms adequately controlled. Restart at 50% of current dose. If symptoms persist despite above measure, discontinue dexamethasone and do not resume.
Musculoskeletal	≥Grade 2 muscle weakness symptomatic and interfering with function but not interfering with activities of daily living	Decrease dexamethasone dose by 25%. If weakness persists despite above measures, decrease dose to 50% of initial dose. Discontinue dexamethasone and do not resume if symptoms persist despite 50% reduction.
Metabolic	≥Grade 3 hyperglycemia	Treatment with insulin or oral hypoglycemic agents as needed. If uncontrolled despite above measure, decrease dose by 25% decrements until levels are satisfactory.

NCI-CTCAE = National Cancer Institute Common Terminology Criteria for Adverse Events

Dexamethasone Toxicity Management Chart

5.6 Criteria for Permanent Discontinuation of Study Drug(s)

Subjects who are experiencing a clinical benefit should remain on study if possible, unless significant toxicity puts the subject at risk, routine noncompliance puts the study outcomes at risk, the subject withdraws consent, or one of the treatment discontinuation reasons referred to in [Section 5.5](#) occurs.

5.7 Use of Concurrent/Concomitant Medications

Throughout the study, investigators may prescribe any concomitant medications or treatments deemed necessary to provide adequate supportive care except for those listed in [Section 5.9](#), Prohibited Therapies. The principal investigator must be notified in advance (or as soon as possible thereafter) of any instances in which prohibited therapies are administered. Systemic use of the following concomitant medications will be collected in the CRF and recorded in the source documents beginning with signing of the ICF to 30 days after the last dose of the last study treatment or until the start of next-line anticancer treatment, if earlier: growth factors, transfusions, anti-infective medications (antibacterials, antivirals, and antimycotics), steroids, anti-arrhythmic medications and other cardiac supportive therapy, anti-epileptic medications, centrally acting psychiatric medications, anti-histamines and other medications targeting post-administration systemic reactions, and any anticancer therapy (including radiation).

Recommended Therapies

Prophylaxis for Bacterial Infection

Prophylaxis for bacterial infections should be considered per institutional guidelines and treating physician preference, especially for subjects with a history of recurrent bacterial infections or severe hypogammaglobulinemia.

Prophylaxis for Herpes Zoster Reactivation

Prophylaxis for herpes zoster reactivation is recommended unless contraindicated.

Prevention of Steroid Induced Gastritis

Dexamethasone and other steroids may induce gastritis. Medications to prevent gastritis are permitted per institutional guidelines, for example proton pump inhibitors (omeprazole or equivalent) or sucralfate, or H2 blockers (ranitidine or equivalent).

Management of Hepatitis B Virus Reactivation

Primary antiviral prophylaxis is permitted as per local standard of care. Per protocol, HBV DNA testing by PCR is mandatory for subjects at risk for HBV reactivation see Section 6.3

For subjects who are diagnosed with HBV reactivation while on treatment, study treatment should be interrupted until the infection is adequately controlled. If the benefits outweigh the risks, study treatment may be resumed with concomitant antiviral prophylaxis as per local standard of care. Consult a liver disease specialist as clinically indicated.

Permitted Therapies

In addition, subjects are to receive full supportive care. The following medications and supportive therapies are examples of support therapies that may be used at any time during the study:

- Antiviral medications should be considered per institutional guidelines.
- Colony stimulating factors and erythropoietin may be used as needed at the discretion of the treating provider (except for Cycle 1 when they can only be used if patient develops \geq Grade 3 neutropenia or \geq Grade 3 anemia respectively rather than pre-emptively to avoid interference with DLT monitoring in Cycle 1)
- Transfusion of platelets and RBCs per institutional goals
- It is important to prevent constipation (eg, adequate hydration, high-fiber diet, and stool softeners if needed).
- Adequate hydration is recommended for prevention of myeloma-related kidney disease.
- Intravenous immunoglobulin (IVIG) may be considered for subjects with recurrent infection related to hypogammaglobulinemia.
- Prophylactic antiemetics, with the exception of corticosteroids
- Loperamide is recommended for the treatment of diarrhea, starting at the time of the first watery stool. The loperamide dose and regimen is according to institutional guidelines. Prophylactic loperamide is not recommended.

5.8 Dietary Restrictions

There are no specific dietary restrictions for study participants.

5.9 Prohibited Medications

Concomitant administration of any other antineoplastic therapy for the intention of treating multiple myeloma is prohibited, including medications that target CD38, as well as medications used for other indications that have anti-myeloma properties (for example, interferon). Any non-study chemotherapy, anticancer immunotherapy, experimental therapy, or radiotherapy are prohibited while the subject is receiving azacitidine treatment.

Concomitant participation in an interventional clinical trial(s) or use of investigational agent(s) as well as medical devices is prohibited. Administration of commercially available agents with activity against or under investigation for multiple myeloma, including systemic corticosteroids (>10 mg prednisone per day or equivalent) (other than those given for IRRs as described in [Section 5.1.1.3](#), Management of Injection-Related Reactions) should be avoided. Nonsteroidal anti-inflammatory agents should be avoided to prevent myeloma-related kidney disease.

Typically, IV contrast is not used in CT scanning of subjects with secretory multiple myeloma because of the risk to the kidney. If administration of IV contrast is necessary, then adequate precautions including hydration are indicated.

6 Study Procedures and Schedule of Events

The study-specific procedures and assessments are detailed in this section and outlined in the Study Procedures and Schedule of Events.

Screening assessments must be performed within 28 days prior to the first dose of investigational product, unless otherwise noted. Any results falling outside of the reference ranges may be repeated at the discretion of the investigator.

All on-study visit procedures are allowed **a window of ± 7 days** unless indicated otherwise on Table 6.1. Treatment or visit delays for public holidays or weather conditions do not constitute a protocol violation.

6.1 Study Calendar

Period/ Procedure	Screening	Cycle 1 ^a (Pre- Induction Phase)	Cycle 1-2 ^a (Induction Phase)				Cycle 3 ^a (Consolidation Phase)				Cycle 4 ^a (Consolidation Phase)				Cycle 5-6 ^a (Consolidation Phase)				Cycle 7 ^a and Onwards (Maintenance Phase)	End of Treatment	Follow-up ^t	
Study Day/Visit Day	D -27 to D-8	D -7 to D-3	D1 (± 1 day)	D8 (± 1 day)	D15 (± 1 day)	D22 (± 1 day)	D1 (± 2 days)	D8 (± 2 days)	D15 (± 2 days)	D22 (± 2 days)	D1 (± 2 days)	D8 (± 2 days)	D15 (± 2 days)	D22 (± 2 days)	D1 (± 2 days)	D8 (± 2 days)	D15 (± 2 days)	D22 (± 2 days)	D1 (± 3 days)			
Study Treatment/Drug																						
Daratumumab ^b			x	x	x	x	x	x	x	x	x	x	x	x	x	x	x	x	x			
Azacitidine ^c		x				x			x				x		x		x		x			
Dexamethasone ^d			x	x	x	x	x	x	x	x	x	x	x	x	x	x	x	x	x			
Administrative Procedures																						
Informed Consent	x																			x		
Clinical Evaluation																						
Physical Exam	x	x	x				x				x				x				x			
Medical History	x																					
Vital signs	x	x	x	x	x	x	x	x	x	x	x	x	x	x	x	x	x	x	x	x		
Weight/height ^e	x	x	x	x	x	x	x	x	x	x	x	x	x	x	x	x	x	x	x	x		
Concomitant medications	x																					
AE assessment ^f	x																					
Performance status ^g	x	x	x				x				x				x				x			
Laboratory Assessments																						
Pregnancy Test ^h	x		x				x				x				x				x	x		
Type and Screen ⁱ	x																					
Hepatitis B (HBV) Serology ^j	x																					
HBV DNA Testing ^k	x																		x	x		
Blood	x	x	x	x	x	x	x	x	x	x	x	x	x	x	x	x	x	x	x	x		

Chemistry ^l																				
Hematology ^m	x	x	x	x	x	x	x		x	x	x		x	x	x	x	x	x	x	
Disease Evaluation^m																				
Immunoglobulin _{sⁿ}	x	x	x				x				x			x				x		
Serum M protein ^o	x	x	x				x				x			x				x		
sFLC ^p	x	x	x				x				x			x				x		
serum IFE ^q	x	x	x				x				x			x				x		
Urine M protein (24 hour urine) ^r	x																	x		
Skeletal Survey	Only as clinically indicated by standard of care																			
PET/CT/MRI	Only as clinically indicated by standard of care																			
Study Procedure/Correlative Studies																				
Bone Marrow Biopsy ^s	x		x																	

^a **Cycle:** Every cycle is 28 days (except for Cycle 1 which extends from day -7 to day 28). The treatment window is \pm 1 days for induction phase, \pm 2 days for consolidation phase, \pm 3 days for maintenance phase

^b **Daratumumab:** Daratumumab dose scheduling, pre-medications, dose modification, and DLTs are detailed in Section 5.

^c **Azacitidine:** Azacitidine dose scheduling, dose modification, and DLTs are detailed in Section 5. Azacitidine will be given for 5 consecutive days starting Cycle 1 day -7 to day -3, Cycle 1-2 Day 22 – 26, Cycle 5 and onwards Day 1-5

^d **Dexamethasone:** Dexamethasone 40 mg PO (or IV if PO is not available) weekly for Cycle 1 and 2. This dose may be reduced or stopped after Cycle 2 on both non-daratumumab administration weeks and on daratumumab administration weeks (as premedication) based on investigator's discretion. Further dose reduction is permitted based on dose modification criteria outlined in [Section 5.5](#).

^e **Weight/height:** Height is required at screening/baseline only. Weight is required at screening and with every daratumumab and first day out of 5 consecutive days of azacitidine administration

^f **AE assessment:** All AEs including adverse events of new onset as well as worsening signs and symptoms are to be reported from the signing of the informed consent to 30 days following the last administration of study treatment. After the 30 days all ongoing related non-serious AEs, ongoing SAE, and new related AE/SAEs are to be followed up to resolution or stabilization.

^g **Performance Status:** This will be measured by ECOG

^h **Pregnancy Test:** Women of child bearing potential must have a negative serum pregnancy within 7 days prior to first study drug administration and D1 of every cycle of treatment starting Cycle 2 (does not need to be performed Cycle 1 Day 1) and at the EOT visit as part of standard of care.

ⁱ Type and Screen: Type and screen study must be done at the time of screening

^j **Hepatitis B (HBV) Serology:** Local testing for hepatitis B surface antigen (HBsAg), hepatitis B surface antibody (Anti-HBs), and hepatitis B core antibody (Anti-HBc).

^k **HBV DNA Testing:** For subjects with serologic evidence of resolved HBV infection (i.e., positive Anti-HBs or positive Anti-HBc) at Screening, HBV DNA testing by PCR must be performed locally. For these patients, HBV DNA testing PCR must be done Q12W during treatment, at the End of Treatment Visit, and Q12W for up to 6 months after the last dose of study treatment.

^l **Blood chemistry:** To be done at screening/baseline, then within 3 days prior to every daratumumab administration and cycle of azacitidine, at the EOT visit, and as clinically

indicated. Blood chemistry includes: SGOT (AST), SGPT (ALT), total bilirubin, alkaline phosphate, lactate dehydrogenase (LDH), sodium, potassium chloride, bicarbonate/carbon dioxide, calcium, magnesium, phosphate, uric acid, blood urea nitrogen (BUN), serum creatinine, albumin, and total protein

^m **Hematology:** To be done at screening/baseline and then within 3 days prior to every daratumumab administration and cycle of azacitidine, at the EOT visit, and as clinically indicated. Hematology includes hemoglobin, hematocrit, RBC, WBC with differential, and platelet counts.

^{n-r} **Disease evaluations:** All lab tests including M-protein quantification (serum and 24-hour urine), immunoglobulins (IgG, IgA, IgM), serum immunofixation, serum free light chains should be performed at screening/baseline. Serum M-protein quantification, immunoglobulins, serum immunofixation, and serum free light chains should also be performed on Cycle 1 D -7 (unless completed within 14 days of this day during screening phase) and every cycle on D1 starting Cycle 2 (Do not need to be performed Cycle 1 Day 1). If UPEP is positive at screening, then repeat UPEP can be done at investigator's discretion. All radiologic assessments are to be performed as clinically indicated and not required by the study. Response is assessed on the basis of clinical and laboratory findings on D1 of every cycle starting C2 prior to study drug administration, whenever disease progression is suspected (eg, symptomatic deterioration) and at the EOT visit. The availability of the results must not prevent the initiation of the next cycle. Response will be assessed against baseline values obtained during screening.

^s **Bone Marrow Biopsy:** Bone marrow biopsy for correlative studies will be performed prior to C0, D-7 (within 14 days of first azacitidine dose) and again at C1, D1 (**or after completion of first 5 days of azacitidine and prior to first daratumumab administration**) and only as clinically indicated at time of progression (though not required by study)

^t **Disease assessments during follow-up period:** are only required for patients with PR or better who have discontinued treatment for reasons other than disease progression and have not yet started treatment with another anti-cancer therapy. Patients will be followed every month for progression during this period. Disease assessments required every month include evaluation of serum M-protein, serum free light chains, and serum immunoglobulins. A bone skeletal survey and PET/CT/MRI are only required if clinically indicated to confirm response or progression according to IMWG criteria. Disease assessments are not required in the follow-up period by this study for patients who have discontinued treatment due to progression or once patients starts treatment with another anti-cancer therapy. For patients who are off study due to disease progression, they will receive a phone call at minimum per study every 4 weeks for one year post last study drug treatment to assess survival

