3.2 Eligibility Criteria

Inclusion Criteria

1. Age ≥ 18 years
2. Patients must have a known diagnosis of multiple myeloma with evidence of measurable disease, AND have evidence of disease progression based on IMWG criteria⁵⁵.
 - o Serum M-protein ≥ 0.5 g/dL, or urine M-protein ≥ 200 mg/24 hours. OR
 - o In the absence of measurable M-protein, Serum immunoglobulin free light chain ≥ 10 mg/dL, and abnormal serum immunoglobulin kappa lambda free light chain ratio.
3. Relapsed from or refractory to 2 or more different prior therapies, including immunomodulatory drugs (IMiDs; eg, thalidomide, lenalidomide) and proteasome inhibitors, chemotherapy-based regimens, monoclonal antibodies, or autologous stem cell transplantation (ASCT).
 - o Relapse is defined as progression of disease after an initial response (MR or better) to previous treatment, more than 60 days after cessation of treatment
 - o Refractory disease is defined as $<25\%$ reduction in M-protein or progression of disease during treatment or within 60 days after cessation of treatment
4. Prior exposure to daratumumab, with most recent dose being at least 6 months prior to trial enrollment
5. ECOG performance status <2 (Karnofsky $>60\%$ (see Appendix 1)
6. Demonstrates adequate organ function as defined below within 7 days of first dose of drug:

Adequate bone marrow function:

absolute neutrophil count	$\geq 1,500/\text{mcL}$
platelets	$\geq 75,000/\text{mcL}$

Adequate hepatic function:

total bilirubin	within normal institutional limits, unless elevated due to Gilbert's syndrome and direct bilirubin is within normal limits
AST(SGOT)	$\leq 3 \times$ institutional upper limit of normal
ALT(SGPT)	$\leq 3 \times$ institutional upper limit of normal

Adequate renal function:

creatinine	$\leq 1.5 \times$ within institutional upper limit of normal
------------	--

OR

creatinine clearance

GFR \geq 60 mL/min/1.73 m², calculated using the Cockcroft-Gault equation, unless data exists supporting safe use at lower kidney function values, no lower than 30 mL/min/1.73 m²

7. Life expectancy of at least 3 months.
8. Women of childbearing potential must have at least one negative highly sensitive serum (β eta-human chorionic gonadotropin [β eta-hCG]) during screening, within one week prior to the first dose of any component of study treatment
9. Before enrollment, a woman must be either:
 - a. Not of childbearing potential defined as:
 - Postmenopausal:

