Subjects with platelet counts $\leq 30,000/\mu\text{L}$ at the beginning of any cycle will be required to have platelet assessment 2 times per week until the end of treatment cycle. Any patient with platelets $> 30,000/\mu\text{L}$ at the beginning of any cycle who develops platelets $\leq 20,000/\mu\text{L}$ at any point during cycle should begin having platelets evaluated two times per week each cycle until patient has a cycle where nadir is $> 20,000/\mu\text{L}$. If Grade 4 neutropenia, assess ANC every 2-3 days until ANC $\geq 0.5 \times 10^9/\text{L}$ and at least weekly thereafter until ANC $\geq 1.0 \times 10^9/\text{L}$.

Otherwise will plan to check complete blood count and chemistry panel with every daratumumab administration and every cycle of azacitidine.

Cycle 1 Day -7 to -3

- History and Physical Examination
- Weight
- Vital Signs*
- Performance Status (ECOG)
- AE/SAE assessment
- Concomitant medications.
- Laboratory Assessments:
 - Blood Chemistry (not required to be repeated if screening labs were performed within 3 days prior to first study drug administration),
 - Hematology (not required to be repeated if screening labs were performed within 3 days prior to first study drug administration),
- Disease assessment (not required to be repeated if screening labs were performed within 14 days prior to first study drug administration)
 - M-protein quantification (serum)
 - Serum free light chain levels
 - Immunoglobulin quantification
 - Serum IFE
- **Administration of azacitidine 75 mg/m²***

*Occur daily Day -7 to -3 as clarified in footnote of table, while the other items only needed on Day -7

Cycle 1, Day 1

- Physical Examination
- Weight.
- Vital Signs.
- Performance Status (ECOG)
- AE/SAE assessment
- Concomitant medications.
- Laboratory Assessments:
 - Blood Chemistry (not required to be repeated at Cycle 1 if labs were performed within 3 days prior to first study drug administration),
 - Hematology (not required to be repeated at Cycle 1 if labs were performed within 3 days prior to first study drug administration)
- Correlative Study procedure: Bone Marrow Biopsy # 2 prior to daratumumab first dose
- **Administration of daratumumab 1800 mg subcutaneous**
- **Administration of dexamethasone 40 mg PO/IV (32 mg on Day 1, 4 mg on Day 2 and Day 3)**

Cycle 1, Day 8 (repeat same Cycle 1, Day 15, Cycle 2, Days 8 and 15, Cycles 3-6, Day 15)

- Weight.
- Vital Signs.
- AE/SAE assessment
- Concomitant medications.

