Partial response (PR)	
≥50% reduction of serum M-protein and reduction in 24-hour urinary M-protein by ≥90% or to <200 mg/24 hours
 
If the serum and urine M-protein are not measurable, a decrease of ≥50% in the difference between involved and uninvolved FLC levels is required in place of the M-protein criteria.
 
If serum and urine M-protein are not measurable, and serum FLC assay is also not measurable, ≥50% reduction in bone marrow PCs is required in place of M-protein, provided baseline bone marrow PC percentage was ≥30%.
 
In addition to the above criteria, if present at baseline, a ≥50% reduction in the size of soft tissue plasmacytomas is also required.

Stable disease (SD)	Not meeting criteria for CR, VGPR, PR, or PD
Progressive disease (PD) ^c	
Increase of 25% from lowest response value in any one of the following:
 
Serum M-component (absolute increase must be ≥0.5 g/dL)
 
Urine M-component (absolute increase must be ≥200 mg/24 hours)
 
Only in subjects without measurable serum and urine M-protein levels: the difference between involved and uninvolved FLC levels (absolute increase must be >10 mg/dL)
 
Only in subjects without measurable serum and urine M-protein levels and without measurable disease by FLC levels, bone marrow PC percentage (absolute percentage must be ≥10%)
 
Bone marrow PC percentage: the absolute percentage must be >10%
 
Definite development of new bone lesions or soft tissue plasmacytomas or definite increase in the size of existing bone lesions or soft tissue plasmacytomas
 
Development of hypercalcemia (corrected serum calcium >11.5 mg/dL or 2.8 mmol/L) that can be attributed solely to the PC proliferative disorder

Relapse from CR	Any one or more of the following: Reappearance of serum or urine M-protein by immunofixation or electrophoresis. Development of ≥5% plasma cells in the bone marrow. Appearance of any other sign of progression (ie, new plasmacytoma, lytic bone lesion, or hypercalcemia)

FLC = free light chain; IMWG = International Myeloma Working Group; M-protein = monoclonal paraprotein; PC = plasma cell.

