Disease progression must be consistently documented using the criteria in table in [Section 7.1.1](#). Disease progression based on 1 of the laboratory tests alone must be confirmed by at least 1 repeat investigation. Clinical judgment should prevail; however, repeat assessments after 1 to 3 weeks can be used as a general guideline. Disease progression based on imaging, bone marrow plasma cell percentage, or hypercalcemia (not attributable to any other cause) do not need to be confirmed. Bone marrow biopsy to assess morphology (aspirate and biopsy) at the time of progression will be at the discretion of the individual provider and not required by the study.

For subjects who discontinue study treatment before disease progression, disease evaluations should continue to be performed as described every 4 weeks until confirmed disease progression, death, the start of a new treatment for multiple myeloma, withdrawal of consent for study participation, or the end of study, whichever occurs first.

Methods of Response Evaluation

Response evaluation will include:

- M-protein quantification (serum and 24-hr urine)
- Serum free light chain (FLC) levels
- Bone marrow biopsy/aspiration (not required)

Myeloma Protein Measurements in Serum and Urine

Blood and 24-hour urine samples will be collected for serum quantitative IgGs, serum and urine M-protein measurements, serum and urine IFE measurements, and serum FLC assay in screening phase (within 28 days of first azacitidine administration). If urine samples cannot be collected, then serum markers will be used alone. Serum quantitative immunoglobulins, serum M-protein measurements, serum IFE, and serum FLC assay will be performed on Cycle 1 Day -7 (prior to first azacitidine dose), unless screening disease evaluation labs were performed within 14 days prior to this first azacitidine administration, and every subsequent cycle on D1 starting cycle 2 (disease evaluation labs do not need to be repeated on Cycle 1 Day 1) until off study and at EOT.

Blood (and 24-hour urine, as determined by the treating physician) samples for disease evaluation will be collected until the development of confirmed disease progression. Progression of disease based on serum markers will need to be confirmed by at least 1 repeat investigation. Progression of disease based on urine markers does not need to be confirmed. Clinical judgment should prevail; however, repeat assessments after 1 to 3 weeks can be used as a general guideline.

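### Where screening disease labs are more than 14 days old, response is judged against them although fresh serum values are taken before the first azacitidine dose

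*Combined protocol and SAP*

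**What the plan says.** Footnotes n-r of the study calendar (Section 6.1) require all disease markers at screening. The serum markers "should also be performed on Cycle 1 D -7 (unless completed within 14 days of this day during screening phase"). The same footnote closes by fixing the reference for response: "Response will be assessed against baseline values obtained during screening".

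Section 7.1 (Myeloma Protein Measurements) repeats the rule: the serum tests "will be performed on Cycle 1 Day -7 (prior to first azacitidine dose), unless screening disease evaluation labs were performed within 14 days". The Cycle 1 Day -7 visit list in Section 6.3 carries the same waiver. Neither place names a baseline.

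Table 7-1 sets the PR threshold at "≥50% reduction of serum M-protein and reduction in 24-hour urinary M-protein by ≥90% or to <200 mg/24 hours", without saying from which value the reduction is counted. Sections 2.3 and 8.2 do not define a response baseline either, so the footnote is the only rule.

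On timing, the calendar gives screening its own column, D -27 to D -8, apart from the Day -7 to Day -3 column. The opening text of Section 6 says "Screening assessments must be performed within 28 days prior to the first dose of investigational product, unless otherwise noted". Sections 6.3 and 7.1 also give 28 days before first azacitidine for the disease labs.

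**The concern.** The protocol treats disease labs more than 14 days old as needing replacement before dosing, but as worded it does not use the replacement as the reference for response. For those patients the measured percentage fall mixes two things: the change before any study drug, and the change on treatment. Only the second is the effect that the overall response rate (ORR) is meant to capture.

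This is a single-arm trial, so no control group shares the same drift. The decision rules in Section 8.1 turn on single patients: stop at 1 or fewer responses in 13, reject the null at 5 or more in 23. Duration of response and the correlation of CD38 change with response use the same response calls.

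**Working it through.** **Design figures.** Inputs from Section 8.1: null 8%, alternative 33%, n1 = 13, stop at ≤1, N = 23, reject at ≥5.

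P(reject) = Σ over x1 = 2..13 of P(X1 = x1) × P(X2 ≥ 5 − x1), with X1 ~ Bin(13, p) and X2 ~ Bin(10, p).

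- At p = 0.08: 0.0302, within the one-sided 5%.
- At p = 0.33: 0.9031, matching the stated 90%.
- A minimax search returns the same design. The choice of baseline enters none of these figures.

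**Who is affected, and by how long a gap.** No repeat is required when the labs are within 14 days, so the affected labs are at least 15 days old on Day -7.

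- Calendar: −7 − (−27) = 20, so 15 to 20 days.
- Text: up to 28 days before first azacitidine, so 15 to 28 days.

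The documents give no count of such patients.

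**Shift in the PR threshold.** Let g be the Day -7 value divided by the screening value. The documents give no M-protein growth rate, so g is assumed.

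- A 50% fall from Day -7 reads, against screening, as 1 − 0.5g.
- The fall from Day -7 needed to be called PR is 1 − 0.5/g.

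| Assumed g | A 50% fall from Day -7 reads as | Fall from Day -7 needed for PR |
|---|---|---|
| 1.10 | 45% | 55% |
| 1.25 | 37.5% | 60% |
| 1.50 | 25% | 67% |
| 0.80 (pre-dose fall) | 60% | 37.5% |

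Over a 20-day gap, the three rises correspond to doubling times of 20 × ln 2 / ln g = about 145, 62 and 34 days, so the last row of the rising cases assumes fast growth. Writing g = 2^(gap/doubling time), a 60-day doubling time needs a fall of 58%, 60% or 64% at gaps of 15, 20 or 28 days. Doubling times of 30 to 180 days and gaps of 15 to 28 days give a range of 53% to 74%.

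**Who changes category.** With a rise, only an affected patient whose best fall from Day -7 lies between 50% and the shifted threshold is lost as a responder. With a fall, the band lies below 50%, and the patient is gained.

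**How much one patient counts.** At a true ORR of 33%:

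- P(exactly 2 of 13) = 78 × 0.33² × 0.67¹¹ = 10.4%.
- P(pass stage 1 and end on exactly 5 of 23) = 8.9%.

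In either case, losing one responder reverses the decision.

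**Illustration only.** These rates are not derived from any baseline shift. If measured ORR were 30% instead of 33%, power would be 84.4%. If the null rate were measured as 10% instead of 8%, the type I error would be 6.8%; at 9% it would be 4.7%.

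**The case against.** A screening baseline is pre-specified and can be defended. PR needs serum and 24-hour urine criteria together. Before treatment, urine is scheduled only at screening, so a screening baseline takes both from one period and from the values that established measurable disease. Taking serum from Day -7 would split the dates in affected patients. That is a real but small cost.

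The wording may also be loose rather than deliberate. The footnote writes screening and baseline as one term, and the 14-day waiver suggests that the two draws were seen as substitutes. A reader might infer that the sponsor chose to discard the Day -7 value; the documents do not show that. If Day -7 was meant to count, the sentence still says otherwise and needs changing.

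Two stronger readings are tempting. One is that the ORR as a whole rests on an out-of-date baseline. It does not: with labs within 14 days, screening is the only baseline required, and in the rest the threshold moves only if the marker moved. The other is that the trial is tilted towards a positive result. Section 3.2 requires that patients "AND have evidence of disease progression based on IMWG criteria", so drift is more likely upward, which works against the regimen. The opposite case is narrowed by exclusion 14, which bars anticancer therapy within 14 days or 5 half-lives of first dose, whichever is longer. It is not removed, because labs drawn 15 or more days before dosing can still predate the end of earlier treatment.

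Finally, ORR is best response over all treatment. A patient near 50% at one visit may fall further later, and deep responders are unaffected.

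**Conclusion.** The point stands for a subset: patients whose screening disease labs are more than 14 days old on Day -7. Their PR threshold includes pre-treatment drift that the protocol already measures and could remove.

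The number of such patients is unknown, so the effect on ORR cannot be estimated from the documents. The 55%, 60% and 67% thresholds rest on assumed rises. The likelier bias is conservative, with some loss of power; the reverse is possible but less likely. Nothing here makes the sample size or the decision rules wrong. The case for acting is that the better rule costs almost nothing, and single responders can decide the trial.

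**What to change.** In footnotes n-r of Section 6.1 and in Section 7.1, define the serum response baseline, for each marker, as the last value on or before the first azacitidine dose: Day -7 when taken, otherwise screening. Keep the screening 24-hour urine value as the urine baseline, and say so.

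Two related clarifications belong with it:

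- Reconcile the calendar's screening window with the 28-day window in the text of Sections 6, 6.3 and 7.1.
- Progression is counted as "Increase of 25% from lowest response value in any one of the following". State whether the Day -7 value can serve as that lowest value.

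The cost is a few sentences. No visit or sample is added, and the 13/23 design is unchanged. The one downside is that serum and urine baselines come from different dates in affected patients. The change should be made before responses are read.
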